### **3. DESCRIPTION OF DESIGN AND TRIAL POPULATION**

#### **3.1 OVERALL TRIAL DESIGN AND PLAN**

This SRD trial is designed as double-blind, randomised within dose group, and placebo-controlled within parallel dose groups.

A total of 24 Japanese healthy male subjects is planned to participate in the trial, according to 3 sequential groups comprising 8 subjects per dose group.

Within each dose group, 6 subjects will receive the active drug and 2 will receive placebo. Only one dose is tested within each dose group.

The dose groups to be evaluated are outlined in Table 3.1: 1 below.

Table 3.1: 1                    Dose groups

Dose Group	1	2	3
Dose (mg)	50	100	200
Number of subjects	8	8	8
Subjects receiving placebo	2	2	2
Subjects receiving active drug	6	6	6

The dose groups will be investigated consecutively in ascending order of doses, maintaining a time interval of at least 7 days between the last drug administration in the previous dose group and the first drug administration of the subsequent dose group.

The decision to proceed to the next dose group will be based upon the safety and tolerability data of the preceding dose groups. The next dose group will only be dose if, in the opinion of the investigator, no safety concerns arose in the preceding dose group(s) (i.e., no dose-limiting events occurred) and if none of the pre-specified trial-specific stopping criteria were met (refer to Section [3.3.4](#)).

A documented safety review must take place prior to randomization in the next group. Furthermore, an unscheduled safety review meeting can be requested anytime for any reasonable cause by the principal investigator (or an authorised deputy) or the sponsor of the study, e.g., because of any unforeseen AEs, etc. Dose escalation will only be permitted if no safety concerns exist in the opinion of the principal investigator (or an authorised deputy) and the sponsor.

The minimum data set for review consists of the following data:

- AEs in the current and preceding dose group(s) (including clinically relevant findings from ancillary safety testing listed below) (Note: AEs may be ongoing at the time of Safety Reviews and AE information may be subject to change prior to Database Lock)
- Results from 12-lead EGG and 4-hours continuous 3-lead ECG monitoring in the current and preceding dose groups.

- Vital signs in the current and preceding dose groups
- Clinical laboratory tests in the current and preceding dose groups
- Check of criteria for stopping subject treatment as per Section [3.3.4.1](#)

The decision to escalate the dose will be made jointly by the Principal Investigator (or an authorised deputy) and the sponsor after in-depth analysis of all available safety data, especially SAEs (if any), AEs, and out-of-range laboratory results (if considered clinically significant). Safety reviews can be conducted verbally (e.g., teleconference) and/or in writing (e.g., encrypted emails, facsimiles correspondences or mails). The CTL is responsible for organization and minutes of the reviews. Minutes will be signed off by the principal investigator (or an authorised deputy) and filed in the investigator site file (ISF) and trial master file (TMF).

An overview of all relevant trial activities is provided in the [Flow Chart](#). For visit schedules and details of trial procedures at selected visits, refer to Sections [6.1](#) and [6.2](#), respectively.

### **3.2 DISCUSSION OF TRIAL DESIGN, INCLUDING THE CHOICE OF CONTROL GROUP**

For SRD trials, the design described in Section [3.1](#) is viewed as favourable under the provision not to expose the subjects involved to undue risks, since the main study objective is to investigate safety and tolerability of BI 730357.

With the rising dose design, double-blind conditions regarding the subjects' treatment (active or placebo) are maintained within each dose group. However, the current dose level will be known to subjects and investigators. The disadvantage of this trial design is a possible observer bias with regard to the dose-depending effects as well as time effects, but it has the virtue of minimizing subject risk by sequentially studying ascending doses. As time-effects are expected to be small relative to the differences between the doses in the broad range investigated, unbiased comparisons between treatments can still be expected.

It is standard in trials involving healthy volunteers to include a placebo group as control for the evaluation of safety and tolerability. Each dose group consists of 8 subjects, with 6 on active treatment, and 2 on placebo. The placebo control group includes all subjects of all dose groups treated with placebo. Six subjects per active treatment group are in general considered as sufficient for the exploratory evaluation of pharmacokinetics.

### **3.3 SELECTION OF TRIAL POPULATION**

It is planned that 24 Japanese healthy male subjects will enter the study. Subjects will be recruited at the trial site.

Only male subjects will be included into the study.

A log of all subjects enrolled into the trial (i.e., having given informed consent) will be maintained in the ISF at the investigational site irrespective of whether they have been treated with investigational drug or not.

### **3.3.1 Main diagnosis for trial entry**

The study will be performed in healthy subjects.

### **3.3.2 Inclusion criteria**

Subjects will only be included into the trial if they meet the following criteria:

1. Healthy male subjects according to the investigator's assessment, based on a complete medical history including a physical examination, vital signs (BP, PR, RR, body temperature), 12-lead ECG, and clinical laboratory tests
2. Japanese ethnicity, according to the following criteria:
  - born in Japan, have lived outside of Japan <10 years, and have parents and grandparents who are Japanese
3. Age of 20 to 45 years (inclusive) at screening
4. BMI of 18.5 to 25.0 kg/m^2 (inclusive) at screening
5. Signed and dated written informed consent in accordance with ICH-GCP and local legislation prior to admission to the trial
6. Male subject who agree to minimize the risk of female partners becoming pregnant by fulfilling any of the following criteria starting from participation to this trial and until 90 days after the trial completion:
  - Use of adequate contraception, e.g., any of the following methods plus condom: combined oral contraceptives, intrauterine device.
  - Vasectomised (vasectomy at least 1 year prior to enrolment)
  - Surgical sterilised (including hysterectomy) of the subject's female partner

### **3.3.3 Exclusion criteria**

Subjects will not be allowed to participate if any of the following general criteria apply:

1. Any finding in the medical examination (including BP, PR or ECG) is deviating from normal and judged as clinically relevant by the investigator
2. Repeated measurement of systolic BP outside the range of 90 to 140 mmHg, diastolic BP outside the range of 50 to 90 mmHg, or PR outside the range of 45 to 90 bpm at screening
3. Any laboratory value outside the reference range that the investigator considers to be of clinical relevance at screening
4. Any evidence of a concomitant disease judged as clinically relevant by the investigator
5. Gastrointestinal, hepatic, renal, respiratory, cardiovascular, metabolic, immunological or hormonal disorders
6. Cholecystectomy and/or surgery of the gastrointestinal tract that could interfere with the pharmacokinetics of the trial medication (except appendectomy and simple hernia repair)

Proprietary confidential information © 2018 Boehringer Ingelheim International GmbH or one or more of its affiliated companies

7. Diseases of the CNS (including but not limited to any kind of seizures or stroke), and other relevant neurological or psychiatric disorders, including but not limited to mood disorders and any history of suicidality
8. History of relevant orthostatic hypotension, fainting spells, or blackouts
9. Chronic or relevant acute infections including human immunodeficiency virus (HIV), viral hepatitis, syphilis and/or tuberculosis
10. History of relevant allergy or hypersensitivity (including allergy to the trial medication or its excipients)
11. Use of drugs within 30 days or 5 half-lives, whichever is longer, prior to administration of trial medication, if that might reasonably influence the results of the trial (including potential for QT/QTc interval prolongation)
12. Participation in another trial where an investigational drug has been administered within 60 days prior to planned administration of trial medication, or current participation in another trial involving administration of investigational drug
13. Previous exposure to BI 730357
14. Smoker (more than 10 cigarettes or 3 cigars or 3 pipes per day)
15. Inability to refrain from smoking on specified trial days
16. Alcohol abuse (consumption of more than 30 g per day for males)
17. Drug abuse or positive drug screening
18. Whole blood donation of more than 200 mL within 30 days or 400 mL within 12 weeks, or plasmapheresis and platelet apheresis within 2 weeks prior to administration of trial medication, or intended donation during the trial
19. Intention to perform excessive physical activities within one week prior to administration of trial medication or during the trial
20. Inability to comply with dietary regimen of trial site
21. A marked baseline prolongation of QT/QTc interval (such as QTc intervals that are repeatedly greater than 450 msec) or any other relevant ECG finding at screening
22. A history of additional risk factors for Torsades de Pointes (such as heart failure, hypokalemia, or family history of Long QT Syndrome)
23. Subject is assessed as unsuitable for inclusion by the investigator, for instance, because considered not able to understand and comply with study requirements, or has a condition that would not allow safe participation in the study

For study restrictions, refer to Section [4.2.2](#).

### **3.3.4 Withdrawal of subjects from treatment or assessments**

Subjects may discontinue trial treatment or withdraw consent to trial participation as a whole ('withdrawal of consent') with very different implications; please refer to Section [3.3.4.1](#) and [3.3.4.2](#) below.

If a subject is removed from or withdraws from the trial prior to the first administration of trial medication, the data of this subject will not be entered in the case report form (CRF) and will not be reported in the clinical trial report (CTR). If a subject is removed from or withdraws from the trial after the first administration of trial medication, this will be

Proprietary confidential information © 2018 Boehringer Ingelheim International GmbH or one or more of its affiliated companies

documented and the reason for discontinuation must be recorded in the CRF; in addition, the data will be included in the CRF and will be reported in the CTR.

At the time of discontinuation, a complete end of study examination will be performed, if possible, and the information will be recorded in the CRF. If the discontinuation occurs before the end of the REP (refer to Section [1.2.6](#)), the discontinued subject should if possible be questioned for AEs and concomitant therapies at or after the end of the REP in order to ensure collection of AEs and concomitant therapies throughout the REP, if not contrary to any consent withdrawal of the subject.

### 3.3.4.1 Discontinuation of trial treatment

An individual subject will discontinue trial treatment if:

- The subject wants to discontinue trial treatment, without the need to justify the decision
- The subject has repeatedly shown to be non-compliant with important trial procedures and, in the opinion of both, the investigator and sponsor representative, is not willing or able to adhere to the trial requirements in the future
- The subject needs to take concomitant medication that interferes with the investigational medicinal product or other trial treatment
- The subject can no longer receive trial treatment for medical reasons (such as surgery, AEs, or diseases)
- An AE or clinically significant laboratory change or abnormality occurs that the investigator assesses as warranting not administering trial medication. This may include cases of sustained symptomatic hypotension (BP <90/50 mmHg) or hypertension (BP >180/100 mmHg), clinically relevant changes in ECG requiring intervention, or unexplained hepatic enzyme elevations at any time during the trial
- The subject has an elevation of aspartate transaminase (AST) and/or alanine transaminase (ALT)  $\geq$ 3-fold upper limit of normal (ULN) and an elevation of total bilirubin  $\geq$ 2-fold ULN (measured in the same blood sample), an elevation of ALT and/or AST  $\geq$ 10-fold ULN, and/or needs to be followed up according to the DILI checklist provided in the ISF

In addition to these criteria, the physician may discontinue subjects at any time based on his or her clinical judgment.

Even if the trial treatment is discontinued, the subject remains in the trial and, given his/her agreement, will follow up as outlined in the [Flow Chart](#) and Section [6.2.3](#).

### 3.3.4.2 Withdrawal of consent to trial participation

Subjects may withdraw their consent to trial participation at any time without the need to justify the decision. If a subject wants to withdraw consent, the investigator should be involved in the discussion with the subject and explain the difference between trial treatment discontinuation and withdrawal of consent to trial participation, as well as explain the options

Proprietary confidential information © 2018 Boehringer Ingelheim International GmbH or one or more of its affiliated companies

for continued follow up after trial treatment discontinuation, please refer to Section [3.3.4.1](#) above.

### **3.3.4.3 Discontinuation of the trial by the sponsor**

BI reserves the right to discontinue the trial overall or at a particular trial site at any time for any of the following reasons:

- New toxicological findings or SAEs invalidate the earlier positive benefit-risk-assessment. More specifically, the trial will be terminated if more than 50% of the subjects show drug-related and clinically-relevant AEs of moderate or severe intensity, or if at least one drug-related serious AE is reported that is considered to be unacceptable
- The expected enrolment goals overall or at a particular trial site are not met
- Violation of Good Clinical Practice (GCP), or the clinical trial protocol (CTP), or the contract with BI by a trial site or investigator, disturbing the appropriate conduct of the trial
- The sponsor decides to discontinue the further development of the investigational product
- Dose escalation will be stopped as soon as at least 2 subjects at one dose level on active drug showed relevant individual QT prolongation, i.e., a QTc increase of greater 60 milliseconds from baseline in connection with absolute QT or QTc greater than 500 milliseconds, which has been confirmed by a repeat ECG recording

The investigator/the trial site will be reimbursed for reasonable expenses incurred in case of trial termination (except in case of the third reason).

For the following scenario further enrolment randomisation into the trial and treatment of already randomised subjects will be interrupted by the sponsor once the sponsor becomes aware:

- Two SAEs in two different subjects in the same system-organ-class, confirmed by both the investigator and sponsor as having a reasonable causal relationship to the trial medication administration.
- Two 'severe' non-serious AEs in two different subjects in the same cohort, independent of within or not within the same system-organ-class, confirmed by both the investigator and sponsor as having a reasonable causal relationship to the trial medication administration.

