##### Drug-related risks and safety measures

The nature of the target and the mechanism of action of BI 730357 are well understood from preclinical models. The safety, tolerability, and PK exposure following single-dose administration of BI 730357 have already been established in first-in-human trial 1407.1, at dose levels up to 800 mg, 4-fold higher than the maximum dose level (200 mg) to be evaluated in the current trial. Furthermore, since this is not a First-in-Human trial, the risk is relatively lower.

The pharmacological effects of BI 730357 are dose dependent and no evidence for prolonged or irreversible effects has been observed. Single dose administration of dose levels up to 800 mg BI 730357 are supported by preclinical safety data.

- Extensive safety laboratory testing will be performed with special focus on full blood exam (refer to [Flow Chart](#)).
- A thorough ECG monitoring including 4-hours continuous 3-lead ECG measurement for at least 15 min before drug administration (for baseline assessment) and for 4 hours following drug administration to cover the anticipated period of highest drug exposure, and additional repeated single 12-lead ECGs over 48 hours (during hospital stay) following drug administration. Dose escalation would be stopped as soon as at

least 2 subjects at one dose level showed relevant QT prolongation (refer to Section 3.3.4.3 for details).

- Prior to each dose escalation, a documented safety review will be performed by the principal investigator and the sponsor (clinical trial leader [CTL]). For details, refer to Section [3.1](#).
- Subjects will be hospitalized on Day -1 (one day before drug administration) and will be discharged on Day 3 only after a formal assessment and confirmation of fitness by an investigator or qualified designee. During in-house confinement, subjects will be under close medical observation and thoroughly monitored for both, expected and unexpected AEs.
- Only if the respective dose of BI 730357 was safe and showed acceptable tolerability and if no stopping criterion was met (refer to Section [3.3.4.3](#)), the next higher dose will be given at least 7 days later (referring to the 1st subject of each dose group).

Since preclinical data indicate that BI 730357 has potential for phototoxicity, subjects will be advised to apply protection measures such as sunscreen, and solarium radiation are prohibited during this clinical trial until the end of the respective follow-up period.

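### Within a dose group, two related severe non-serious AEs force an interruption, but two related SAEs in different organ classes, or one event of each kind, do not (Protocol 3.3.4.3)

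*Protocol*

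**What the plan says.** Protocol 3.3.4.3 ends with two events after which further randomisation stops and "treatment of already randomised subjects will be interrupted by the sponsor once the sponsor becomes aware":

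- Trigger 1: "Two SAEs in two different subjects in the same system-organ-class". It is not limited to one cohort.
- Trigger 2: "Two 'severe' non-serious AEs in two different subjects in the same cohort, independent of within or not within the same system-organ-class".

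Both require the investigator and the sponsor to confirm a reasonable causal relationship.

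Earlier in the same section the trial is to be terminated in two further situations: when more than half of the subjects have drug-related, clinically relevant AEs of moderate or severe intensity, or "if at least one drug-related serious AE is reported that is considered to be unacceptable". A separate QT rule stops dose escalation only.

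Section 3.1 adds a gate between groups ("A documented safety review must take place prior to randomization in the next group") and an optional review within a group ("an unscheduled safety review meeting can be requested anytime for any reasonable cause"). Section 5.2.6.2.2 requires SAEs to reach the sponsor within 24 hours. Section 8.6 defines a temporary halt by the sponsor.

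**The concern.** The requirement for the same organ class takes some SAE pairs out of trigger 1. The word non-serious takes every SAE out of trigger 2. Within a cohort, two kinds of pair therefore meet neither trigger: two related SAEs in different organ classes, and one related SAE with one related severe non-serious AE in any class.

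The result is an inversion. Suppose two subjects in one group have related severe non-serious AEs: dosing must pause. If one of them is then admitted to hospital, the event becomes serious under 5.2.6.1.2, trigger 2 is no longer met, and trigger 1 is not met either. A worsening has removed a mandatory pause, and the protocol gives no reason for this.

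At stake is the protection of healthy volunteers in the same group who have not yet been dosed, and of any replacement subject, who under 3.3.5 receives the same treatment as the subject replaced.

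**Working it through.** The plan gives no figure to reproduce, and section 7.7 states that the sample size is not based on power. The check is on rule logic, followed by a rough bound on likelihood.

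**1. Rule outcomes.** Take two different subjects, each with one event confirmed as related. Here SAE is a serious event and SEV a severe non-serious AE. Judgement means that the single-SAE termination rule applies, but only if the event is thought unacceptable.

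| Pair | Organ class | Same cohort | Different cohorts |
|---|---|---|---|
| SAE + SAE | same | forced (trigger 1) | forced (trigger 1) |
| SAE + SAE | different | judgement | judgement |
| SAE + SEV | same | judgement | judgement |
| SAE + SEV | different | judgement | judgement |
| SEV + SEV | same | forced (trigger 2) | no two-event rule |
| SEV + SEV | different | forced (trigger 2) | no two-event rule |

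Same cohort: 3 of 6 forced, 3 on judgement. Different cohorts: 1 forced, 3 on judgement, 2 without a rule triggered by two such events. These are counts of rule outcomes, not probabilities.

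**2. Could the more-than-50% rule catch these pairs?** With 8 subjects in a group it needs 5; with 24 overall it needs 13; if only the 6 active subjects of a group count, it needs 4. Two subjects are 2/8 = 25%, 2/24 = 8% or 2/6 = 33%. So it is not reached in a full group. The denominator is not defined, however. If only subjects dosed so far were counted, 2 of 2 (100%) or 2 of 3 (67%) would exceed 50%, while 2 of 4 (50%) would not. Both events would also have to be clinically relevant and at least moderate, and an SAE need not be.

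**3. Who is left undosed.** A group has 8 subjects, 6 active and 2 placebo (section 3.1). After two affected subjects, at most 8 − 2 = 6 are undosed, of whom at most 6 − 2 = 4 are active if both affected subjects were active. The lower limit is 0, if the group is dosed together. If the 50% rule counted subjects dosed so far, and both events were clinically relevant and at least moderate, a pair among the first two or three would end the trial. The gap would then begin at four dosed, leaving 0 to 8 − 4 = 4 undosed.

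The range is assumed, because no within-group schedule is stated. Section 3.1 speaks of an interval between "the last drug administration in the previous dose group and the first drug administration of the subsequent dose group", and section 1.4 gives its interval as "referring to the 1st subject of each dose group". Both wordings allow spread-out dosing within a group but do not establish it; the Flow Chart shows a single approximate dosing time of 09:00.

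**4. Likelihood.** Section 1.2.5 reports no SAEs in the single-dose first-in-human trial, where 54 + 12 = 66 subjects received active drug. The one-sided 95% upper bound per subject is 1 − 0.05^(1/66) = 0.0444. With p = 0.0444 and independent subjects, P(at least 2 of 6 active) = 1 − (1 − p)^6 − 6p(1 − p)^5 = 0.026. Counting only the 54 gives p = 0.0540 and 0.038. These figures cover any SAE, related or not, in any organ class, so the SAE pairs in the gap are a subset. The documents give no rate for severe non-serious AEs, so mixed pairs cannot be bounded.

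**The case against.** The best defence is that the rules are layered. A single related SAE already raises the question of termination, and trigger 1 reaches across cohorts. Severe non-serious AEs have no single-event rule, so they get a wider organ-class condition within one cohort. Judgement also enters the forced triggers, through the confirmation of causality and the grading of intensity.

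Exposure is limited as well. Each subject takes one dose. If a group is dosed together, nobody in it remains to be protected except possible replacements, and replacement is itself a sponsor decision (3.3.5). The next group cannot start without a documented review and the agreement of investigator and sponsor. The introduction to section 8 foresees urgent safety measures by the investigator. Single doses up to 800 mg have been given (section 1.4), and the multiple-dose trial reported no SAEs at up to 400 mg for up to 28 days.

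Most of this stands, and it makes the point minor. It does not remove the inversion. The term unacceptable is undefined, the extra review is optional, a temporary halt is discretionary, and reporting within 24 hours informs the sponsor without pausing dosing. Layering explains why SAEs have a rule of their own. It does not explain why an event that turns serious should cancel a pause.

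**Conclusion.** The inversion holds on the plain text: 3 of 6 same-cohort combinations force an interruption, and the 3 that do not all contain an SAE. The consequence is small, limited to the undosed subjects counted above and any replacements, and the likelihood is low. The likelihood figures assume that the SAE rate in the first-in-human trial carries over to Japanese men and that subjects are independent.

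A reader might infer three stronger things, none of which the documents support:

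- That these pairs have no cover at all. Each contains a related SAE, so the single-SAE termination rule applies, subject to judgement.
- That two events can never reach the more-than-50% rule. Its denominator is undefined, and two of the first two or three dosed subjects could reach it.
- That later dose groups are left unprotected. The review in 3.1 is mandatory before randomisation in the next group, although its outcome also rests on opinion.

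**What to change.** In the second interruption bullet of 3.3.4.3, let the rule open with *Two AEs that are severe or serious* in place of the present reference to severe non-serious AEs. Keep the conditions on two different subjects, the same cohort and any organ class, and the confirmation of causality. Leave the first bullet as it is, so that SAEs in one organ class still count across cohorts.

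Same-cohort combinations that force an interruption rise from 3 of 6 to 6 of 6. Different-cohort combinations stay at 1 of 6, so the remedy is partial by design.

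The cost is one phrase by protocol amendment, with no added procedures or subjects. The downside is a slightly higher chance of a temporary pause, including for SAEs of mild or moderate intensity in unrelated organ classes. With SAEs split into severe and non-severe there are 6 pair types × 2 organ-class states = 12 same-cohort combinations. Those that interrupt rise from 5 to 12, and 4 of the 7 added ones contain a non-severe SAE. Both parties would still have to confirm causality, and an interruption can be lifted. For healthy volunteers with no therapeutic benefit that is a reasonable trade, but it is an optional improvement and not a condition for running the trial.
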